The objective of this study is to investigate blood product use, bleeding events, hospital length of stay, and health care costs in hospitalized patients with cirrhosis and coagulopathy undergoing endoscopy or neurosurgical procedures utilizing ROTEM compared to conventional therapy. Data will be extracted from charts in the electronic medical record (IHIS). Data from charts will be used to construct a secure database of information on risk factors and pre-procedure testing (see Appendix 1). This database will allow analysis of clinical outcomes in patients with cirrhosis undergoing an endoscopic or surgical procedure.

In this prospective study, patients will be randomized into one of two groups:

-Study Group: those who receive blood product transfusions based on ROTEM-guided protocol (Appendix 2). -Control Group: those who receive blood product transfusions based on conventional, laboratory-guided parameters (Appendix 3).

The randomization list will be computer-generated using a balanced allocation ratio of 1:1. The endoscopist or surgeon performing the procedure will be blinded to the patient's group.

B. Hypothesis

The ROTEM- guided transfusion protocol will significantly decrease blood product usage without any increase in procedural bleeding complications versus the conventional, laboratory-based transfusion protocol in patients with cirrhosis undergoing endoscopy and neurosurgical procedures.

C. Objectives

Primary Objective

To compare the total amount of pre-procedure blood products transfused between the ROTEM-guided transfusion protocol and conventional, laboratory-based transfusion protocol in patients undergoing endoscopy and neurosurgical procedures. Endoscopy procedures include esophagogastroduodenoscopy, colonoscopy, flexible sigmoidoscopy, endoscopic retrograde cholangiopancreatography, and endoscopic ultrasound. Neurosurgical procedures may include bedside procedures (e.g. placement of an external ventricular drain or placement of an intracranial pressure monitor), or any neurosurgical cranial or spinal procedure that occurs in the operating room

WEXNER MEDICAL CENTER

during the patient's admission (e.g. craniotomy for evacuation of hematoma or a spinal fusion procedure to address spinal instability).

Secondary Objectives

- 1. Compare the rate of bleeding events between ROTEM vs. conventional therapy:

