 - Clinically significant peri-procedure blood loss as documented by the endoscopist or surgeon performing the procedure
 - Major bleeding during the 24 hours post-procedure, defined as a decrease in hemoglobin of ≥ 2 g/dL or requiring a transfusion of ≥ 2 units of packed red blood cells.
- 2. Compare length of stay between ROTEM vs. conventional therapy
- 3. Compare hospitalization costs between ROTEM vs. conventional therapy

D. Sample

202 patients with cirrhosis and coagulopathy who are undergoing an endoscopic or neurosurgical procedure, at The Ohio State University Wexner Medical Center will be enrolled into the study using the inclusion/exclusion criteria below. Coagulopathy will be corrected by ROTEM-guided transfusion protocol (Appendix 2) or conventional, laboratory-based transfusion protocol (Appendix 3) prior to procedure using a 1:1 randomization.

For the primary aim, a total sample size of 202 patients (101 patients in both the non-ROTEM and ROTEM groups) is required to achieve 80% power for a two-sample t-test to detect a 100% increase in the geometric mean of the non-ROTEM group over the ROTEM group. Significance is defined as a two-sided p-value of less than 0.05. This calculation was based off of pilot data which contained 8 ROTEM and 8 non-ROTEM patients. The secondary aim, demonstrating that the proportion of bleeding events in ROTEM patients is equivalent to or less than the proportion in non-ROTEM patients requires a sample size of 446 patients per group. This calculation assumed that both ROTEM and non-ROTEM patients experience a bleeding event 10% of the time. It was further assumed that the proportion of bleeding events in the ROTEM group will be considered to be equivalent to that of the non-ROTEM group if the proportion is no more than 5% larger. The secondary aim is exploratory in nature for the purposes of this protocol as the sample size for the current study is only 202 patients.

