The requested data fields include demographic data, clinicopathologic data, and procedure/operative reports. Please see Appendix 1 for all variables that will be extracted from charts. Any PHI that is collected as part of this prospective study will be maintained in the secure database.

Standard coagulation tests

Conventional coagulation tests (hemoglobin, platelet count, fibrinogen concentration, INR, aPTT, and PT) will be performed in both groups (ROTEM vs. conventional therapy) at two fixed time points (enrollment and within 3 hours after transfusion [which is also within 12 hours of procedure]) in order to compare both groups reliably. Transfusion of blood products (if indicated per the transfusion protocols) will occur within 24 hours of enrollment in both groups. In the post-procedure setting, tests will be performed if any bleeding occurs per the treating physician's discretion.

ROTEM

ROTEM will be performed according to the manufacturer's instruction, using equipment provided by Tem International GmbH. All tests will be performed at the bedside by a clinical perfusionist or study staff member trained to perform ROTEM. The point of care treatment will be guided with the Spine Surgery Algorithm based on the EXTEM, INTEM, FIBTEM and HEPTEM assays. ROTEM will be performed in both groups (ROTEM vs. conventional therapy) at two fixed time points (enrollment and within 3 hours after transfusion [which is also within 12 hours of procedure]) in order to compare both groups reliably.

The Ohio State University

WEXNER MEDICAL CENTER

F. Data Analysis

We will analyze blood product usage, peri- and post-procedure bleeding events, and hospital length of stay comparing ROTEM-guided transfusion protocol versus conventional, laboratory-based transfusion protocol. We will calculate any significant differences between these two cohorts using standard T-Test and multivariate analysis (ANOVA) with support from our Internal Medicine biostatistician.

All study patients will be continuously monitored by the study PI and sub-I's on the inpatient hepatology services. Safety monitoring will be performed on an ongoing basis throughout the entirety of the study. Based on our retrospective study using ROTEM in liver transplantation, we expect FFP transfusion rate to decrease by 50% and cryoprecipitate transfusion rate to increase in the ROTEM group with an overall decrease in blood product use. We expect bleeding rates to be similar in both groups.

IV. References

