Fibrinogen Pre transfusion	Fibrinogen (number)		
Fibrinogen Post transfusion	Fibrinogen (number)		
International Normalized Ratio (INR) Pre transfusion	International Normalized Ratio (INR) (number)		
International Normalized Ratio (INR) Post transfusion	International Normalized Ratio (INR) (number)		
Procedure performed	esophagogastroduodenoscopy = 1, colonoscopy = 2, neurosurgical procedures = 3, other endoscopy procedures = please type out procedure (e.g. endoscopic ultrasound)		
Blood product use prior to procedure	Number of Units		
Type of blood product given prior to procedure	Fresh Frozen Plasma (FFP) = 1, platelets = 2, cryoprecipitate = 3		
Packed Red Blood Cells (pRBC) use post-procedure	Number of units		
Total blood product use post-procedure	Number of units		
Significant blood loss peri-procedure	No = 0, Yes = 1		
Bleeding event 24 hours post-procedure	No = 0, Yes = 1		
Hospital Length of Stay	Number of Days		
Cost	Total cost of ROTEM reagents and supplies used and		
	lab tests (number)		

Division of Gastroenterolgoy, Hepatology & Nutrition Confidential

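### The 80% power in Protocol III.D belongs to a log-scale t-test, but the endpoint can be zero and III.F names neither a scale nor a zero rule, so the 80% is not established for the analysis as written

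*Protocol*

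**What the plan says.** The primary objective (Protocol III.C) is "To compare the total amount of pre-procedure blood products transfused" between the two transfusion strategies. Appendix 1 records the variable "Blood product use prior to procedure" as a number of units.

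III.D sizes the trial at 202 patients, 101 per group, for 80% power with a two-sample t-test at two-sided 0.05 "to detect a 100% increase in the geometric mean of the non-ROTEM group over the ROTEM group". On the source it says only: "This calculation was based off of pilot data which contained 8 ROTEM and 8 non-ROTEM patients". It gives no SD, no zero share and no rule for zeros.

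Two passages bear on whether zeros occur. III.E (Standard coagulation tests) says: "Transfusion of blood products (if indicated per the transfusion protocols) will occur within 24 hours of enrollment in both groups". III.D says: "Coagulopathy will be corrected by ROTEM-guided transfusion protocol (Appendix 2) or conventional, laboratory-based transfusion protocol (Appendix 3) prior to procedure".

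For the analysis, III.F says: "We will calculate any significant differences between these two cohorts using standard T-Test and multivariate analysis (ANOVA"). It mentions no log transformation, offset or zero rule. The SAP uses Wilcoxon rank-sum tests for product use, but its text concerns liver transplantation (OLT), 34 patients per group, and power for intra-operative blood loss.

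**The concern.** A ratio of geometric means is a difference in mean logs. One untransfused patient makes that arm's geometric mean zero, and the log of that patient's value does not exist. The sizing thus assumes a kind of data that the endpoint definition does not guarantee.

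The analysis section does not close the gap. On raw units, the t-test is a different test from the one that was sized. On logs, it stops at the first zero until someone chooses a rule, and that choice changes the estimated effect. If scale and offset are left open until the data are seen, the primary result can depend on a choice made after the fact, and the advertised 80% describes neither route.

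**Working it through.** **Inputs.** From III.D: n = 101 per group, two-sided alpha 0.05, power 80%, geometric-mean ratio 2 (ln 2 = 0.693). The log SD is not stated. Zero shares and unit distributions below are assumptions.

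**1. Back-solve III.D.** The t-test has noncentrality (ln 2 / SD) × √(101/2) on 200 df. Setting power to 80% gives a standardised difference of 0.396, so SD = 0.693 / 0.396 = 1.75. The stated size is therefore possible, but it cannot be checked without the pilot SD. Power for a ratio of 2 at 101 per group:

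| Log SD | 1.5 | 1.75 | 2.0 | 2.25 |
|---|---|---|---|---|
| Log t-test power | 90% | 80% | 69% | 59% |

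If 1.75 was estimated from 16 pilot patients (14 df, normal logs assumed), its 95% interval runs from 1.75 × √(14/26.12) = 1.28 to 1.75 × √(14/5.63) = 2.76. Power would then lie between 97% and 43%.

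**2. Same inputs, raw units.** I simulated log-normal data with log SD 1.75, ratio 2, no zeros and 101 per group. The log t-test had about 80% power, Wilcoxon about 78% and the untransformed t-test about 34%. The raw-scale loss follows from the implied skewness: CV = √(exp(1.75²) − 1) = 4.5.

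**3. Logs, with zeros possible.** P(at least one zero among 202) = 1 − (1 − p)^202. This is 87% at p = 1% and 98% at p = 2%.

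**4. Effect of an offset.** Assume 20% zeros in the conventional arm, 50% in the ROTEM arm, and U = 1 + Poisson(3) units (mean 4) if transfused. The ratio of arithmetic means is 0.8 / 0.5 = 1.6. With offset c, the difference in mean logs is (0.5 − 0.2) × (E[ln(U + c)] − ln c).

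| Offset c | E[ln(U + c)] − ln c | Log-scale ratio | Log SD | Difference / SD |
|---|---|---|---|---|
| 1 | 1.547 | 1.6 | 0.76 | 0.61 |
| 0.5 | 2.118 | 1.9 | 1.01 | 0.63 |
| 0.1 | 3.615 | 3.0 | 1.68 | 0.65 |
| 0.01 | 5.889 | 5.9 | 2.69 | 0.66 |

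The estimated ratio depends heavily on the offset. Power hardly does: it is about 99% in every row.

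**5. Direction of the power error.** Simulated power at 101 per group, with log-normal units among the transfused (log SD 1.75, ratio 2, ROTEM geometric mean 2 units):

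| Zeros, ROTEM / conventional | Untransformed t | Log t, offset 1 | Log t, offset 0.1 | Wilcoxon |
|---|---|---|---|---|
| 20% / 20% | 27% | 54% | 44% | 42% |
| 40% / 40% | 21% | 36% | 24% | 17% |
| 40% / 20% | 47% | 95% | 97% | 97% |

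Equal zeros in both arms pull power down. Fewer transfused patients in the ROTEM arm push it up for every method that limits the influence of large values.

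**The case against.** The strongest reply is that III.D already names the primary test. The III.F sentence is generic, covering product use, bleeding and length of stay together, so its t-test can be read as the log-scale test of III.D. That reading is reasonable. Under it the scale mismatch goes away, but the zero problem comes fully into play, and the SD is still unreported.

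Second, zeros may be rare: everyone enrolled is coagulopathic and III.D says the coagulopathy will be corrected. The rules that decide this are in Appendices 2 and 3, whose content is not visible in the text reviewed. This stands as a limit on what can be said about frequency. It does not remove the need for a rule, because transfusion remains conditional in both groups and a 1% share is enough to stop the log test. The 87% measures that chance; it does not measure lost power.

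Three stronger readings are tempting and not supported:

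- **The trial is underpowered, with true power near 34%.** That figure holds for one reading of III.F, log-normal data and a back-solved SD. Step 5 shows power can also exceed 80%.
- **The choice of offset makes the required sample size swing widely.** Ratio and SD move together, so step 4 shows power of about 99% at every offset. What changes is the reported effect.
- **An untransformed t-test would be invalid.** In null simulations with 5% to 60% zeros in both arms (1 + Poisson units, mean 4 if transfused), it rejected 4.7% to 5.1% of the time. The issue is which test was powered.

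**Conclusion.** The point holds as a gap between the power statement and the analysis plan for the primary endpoint. The 80% applies to a log t-test on strictly positive values with an unreported SD. It does not carry over to a t-test on raw units (about 34% under III.D's own implied inputs), and a log t-test is not defined for data containing a zero until a rule is written. With zeros, an unstated offset could move the estimated ratio from 1.6 to 5.9 in the assumed 20% versus 50% case.

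The SAP does not settle the matter. Wilcoxon accepts zeros, but the SAP specifies it for a different setting, sample size and powered outcome, and gives no power for this endpoint.

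The central conclusion, that 80% is not established, rests on the documents' text alone. The sizes rest on the back-solved SD of 1.75, log-normality and assumed zero shares, so they show what could happen and do not estimate this trial's power. The gap should be fixed, and rewording plus a restated power calculation is enough.

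**What to change.** In III.F and the SAP, name one primary test of total pre-procedure units that is defined when zeros occur, chosen in advance from the pilot's zero share and SD. Acceptable choices are a log t-test with a pre-stated offset, Wilcoxon rank-sum, an explicitly untransformed t-test, or a log-link count model with robust standard errors. Whichever is chosen, report mean units per arm and their difference or ratio with a 95% confidence interval.

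In III.D, report the pilot's log SD, its zero share and any zero rule used. Restate power at 101 per group for the named test over a range of SDs and zero shares, since the pilot had only 8 patients per arm.

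The cost is rewording and a re-run calculation, with no new data. The restated power may be less favourable, and no test is best in every case. With an assumed 5% versus 20% zeros (conventional versus ROTEM, 1 + Poisson units with mean 4 if transfused), the log t-test has about 79% to 91% power across offsets from 1 to 0.01, the untransformed t-test about 54% and Wilcoxon about 46%. With no zeros and very skewed use, as in step 2, Wilcoxon is far ahead of the untransformed test. The pilot data should therefore guide the choice.

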COVER LETTER

Document date: 3/10/2020

Comparison of Blood Product Use and Bleeding Events During and After Endoscopic or Neurosurgical Procedures in Patients with Cirrhosis and Coagulopathy: Rotational Thromboelastometry Versus Conventional Therapy

NCT02457403

Statistical Analysis

Our sample size of thirty-four patients per group was based on a pilot project at OSUWMC that evaluated a total of sixteen patients. The same variables were studied in the pilot project, but no statistically significant results were found. We powered our study for the primary outcome of intra-operative blood loss based on the results of the pilot data.

Patient characteristics and laboratory values were compared between the two groups. Fisher exact tests were used to test for significant differences between the ROTEM and conventional coagulation groups with discrete variables such as race and gender. With continuous variables that were approximately normally distributed (BMI, MELD, and age), two-sample t-tests were used to test for significant differences between groups. Due to the non-normality of all laboratory values and ICU length of stay, nonparametric Wilcoxon rank-sum tests were used to test for significance.

Blood product usage and blood loss during OLT comparing ROTEM guided transfusion therapy versus conventional coagulation therapy were also analyzed. Due to the non-normality of the data, nonparametric Wilcoxon rank-sum tests were used to test for significant differences between the two groups in terms of the use of the 5 different blood products and blood loss. The sum of pRBCs, FFP, platelets, cryoprecipitate, and Cell Saver in units was used as an indicator of total blood product use. Results are expressed as medians and interquartile ranges. A two-tailed P value <0.05 was considered significant.

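### The 446 per group for the bleeding aim is given without alpha, sidedness or power, and no planned analysis uses its 5-point margin

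*Protocol*

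**What the plan says.** Protocol section III.D (Sample) contains two sample-size calculations in one paragraph.

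- **Primary aim (blood products).** 101 per group "is required to achieve 80% power for a two-sample t-test". Next comes the protocol's only significance rule: "Significance is defined as a two-sided p-value of less than 0.05". The sentence after that returns to the pilot data behind the primary calculation.
- **Bleeding aim.** The goal is to show that the ROTEM proportion "is equivalent to or less than the proportion in non-ROTEM patients", and this "requires a sample size of 446 patients per group". The stated assumptions are that "both ROTEM and non-ROTEM patients experience a bleeding event 10% of the time" and that ROTEM is acceptable "if the proportion is no more than 5% larger". Alpha, sidedness and power are not given. The paragraph ends by calling this aim exploratory, because only 202 patients will be enrolled.

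Section III.B (Hypothesis) pairs lower product use with no increase in procedural bleeding. Section III.F (Data Analysis) names a t-test and ANOVA to look for differences in product use, bleeding events and length of stay. It mentions neither the margin nor a confidence interval. The SAP (Statistical Analysis) ends with "A two-tailed P value <0.05 was considered significant", after a list of tests for differences between groups. It contains no analysis of the proportion of patients with a bleeding event.

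**The concern.** A non-inferiority sample size cannot be interpreted without its error rates. The two natural readings here give different numbers and different decision rules. One-sided 0.05 corresponds to comparing the upper limit of a two-sided 90% interval with the 5-point margin. One-sided 0.025 corresponds to a 95% interval. The only level that the protocol states points to the second, while the figure it prints matches the first.

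What is at stake is how the bleeding result will be read. A margin is set but no analysis uses it, so the default is a test for a difference. With 101 per group, such a test can easily be non-significant when the data are compatible with an increase well beyond 5 points. If the level is left open, the interval could also be chosen after the data are seen.

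**Working it through.** **Inputs.** Event rate 10% in both arms, margin 5 percentage points in one direction, figure 446 per group (all Protocol III.D); allocation "balanced allocation ratio of 1:1" (Protocol III.A). Three assumptions are needed: the 5% is absolute, the 80% power of the primary aim carries over, and the usual convention holds that two-sided 0.05 corresponds to a one-sided 0.025 bound.

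**Formula** (unpooled variance, true difference zero):

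n per group = 2 × p(1 − p) × (z_alpha + z_power)² / margin²

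With p = 0.10 and margin 0.05, the multiplier is 2 × 0.09 / 0.0025 = 72.

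**1. The protocol's figure.** One-sided 0.05, 80% power: 72 × (1.6449 + 0.8416)² = 445.1, rounded up to **446**. This is an exact match.

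**2. Two-sided 0.05 applied as one-sided 0.025.** 72 × (1.9600 + 0.8416)² = 565.1, rounded up to **566**. That is 566/446 = 1.27, or 27% more.

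**3. Other routes to 446.**

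| Method, 80% power | one-sided 0.05 | one-sided 0.025 |
|---|---|---|
| Unpooled | 446 | 566 |
| Farrington-Manning | 457 | 581 |
| Continuity-corrected | 485 | 605 |
| Two one-sided tests (equivalence) | 617 | 757 |

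A superiority test of 10% against 15% gives 686 (two-sided) or 540 (one-sided). A relative 5% margin gives 44,515. At 80% power, only the unpooled one-sided 0.05 formula returns 446. If power is left free, one-sided 0.025 with 70% power gives 72 × (1.9600 + 0.5244)² = 444.4, so 445, one patient away.

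**4. Power.** Power = Φ(0.05/SE − z_alpha), with SE = √(0.18/n).

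- n = 446: SE = 0.02009, 0.05/SE = 2.489. One-sided 0.05: Φ(0.844) = 80%. One-sided 0.025: Φ(0.529) = **70%** (69% by Farrington-Manning).
- n = 101: SE = 0.04222, 0.05/SE = 1.184. One-sided 0.05: Φ(−0.461) = **32%**. One-sided 0.025: Φ(−0.776) = **22%**.

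**5. What 101 per group can show.** If both arms are observed at 10%, the upper limit for the difference is 1.6449 × 4.22 = 6.9 points (90% interval) or 1.9600 × 4.22 = 8.3 points (95%). Both exceed the margin.

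Two hypothetical results with Wald standard errors:

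- *ROTEM 18/101, control 10/101.* Difference 7.9 points, SE = √((0.1465 + 0.0892)/101) = 4.83 points, z = 1.64, two-sided p = 0.10. The difference is non-significant although the estimate lies beyond the margin.
- *ROTEM 9/101, control 11/101.* Difference −1.98 points, SE = √((0.0812 + 0.0970)/101) = 4.20 points. The upper limit is −1.98 + 6.91 = 4.9 points on a 90% interval (inside the margin) and −1.98 + 8.23 = 6.3 points on a 95% interval (outside). The undeclared level decides the conclusion.

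**The case against.** A reader might infer that 446 is wrong and that the protocol's own rule makes 566 the right number. The documents do not support that, for four reasons.

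- The two-sided sentence stands between two sentences about the primary t-test, and the bleeding aim comes afterwards with its own assumptions. Reading the rule as trial-wide is reasonable, but its placement favours the primary aim.
- Neither document says that two-sided 0.05 becomes one-sided 0.025 for a margin question. One-sided 0.05 is a legitimate choice for a one-directional aim.
- The 80% power is stated for the primary aim only, so the link from 446 to one-sided 0.05 is conditional on carrying it over.
- The SAP sentence is weak support. That document describes product use and blood loss during OLT with 34 per group, and its rule follows tests for differences, not a margin test on bleeding events.

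All four points stand. It is also true that the protocol openly discloses the shortfall: 101 per group is far below either figure, so neither number changes enrolment or the primary analysis.

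A further objection is that no error rate is at issue because no margin test is planned. That describes the present plan correctly, but it is a reason to name the analysis. The exploratory label does not stop a non-significant difference from being reported as support for the bleeding half of the hypothesis.

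**Conclusion.** The point holds as a reporting gap, and it is minor. The 446 is a correct figure for inputs that the protocol does not state. With 80% power carried over, those inputs are one-sided 0.05, which neither document declares. Under the only declared level, applied as a one-sided 0.025 bound, the requirement is 566 per group and 446 gives about 70% power. Power at the planned 101 per group is about 32% or 22%, so the trial is unlikely to establish non-inferiority under either reading.

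These results assume 10% events in both arms, an absolute 5-point margin and the unpooled formula. The 27% gap does not depend on the event rate: at 7% the two figures are 322 and 409, and at 11% they are 485 and 615.

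The part that matters for interpretation is the missing link between the margin in III.D and the analysis in III.F. It would be going too far to conclude that the sample size was miscalculated or that more patients are needed.

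**What to change.** 1. Beside the figure in III.D, state alpha, sidedness and power. Either keep 446 and declare one-sided 0.05 with 80% power, or give 566 per group under two-sided 0.05 (one-sided 0.025) with 80% power.
2. In the same place, give the power at 101 per group: about 32% with the first choice, about 22% with the second.
3. In III.F and the SAP, specify that the difference in bleeding-event proportions is reported with the matching two-sided confidence interval (90% for one-sided 0.05, 95% for one-sided 0.025) and compared with the 5-point margin. State that a non-significant test for a difference will not be taken as evidence of no increase in bleeding.

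The cost is a sentence or so of wording and, if the second choice is made, a less favourable stated figure. No further enrolment is asked for, and the aim stays exploratory.

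### No rule for in-hospital deaths in the hospital-stay comparison: on the natural reading an early death counts as a short stay, and the planned data cannot show it

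*Protocol*

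**What the plan says.** The second secondary objective in Protocol section III.C is "Compare length of stay between ROTEM vs. conventional therapy". Section III.F states "We will analyze blood product usage, peri- and post-procedure bleeding events, and hospital length of stay comparing ROTEM-guided transfusion protocol" and follows with the only methods named for these outcomes: "standard T-Test and multivariate analysis (ANOVA) with support from our Internal Medicine biostatistician". It gives no transformation, and no rule for patients who die in hospital.

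Appendix 1, which section III.E presents as the full list of variables taken from the charts, has the entry "Hospital Length of Stay", recorded in days. It has no entry for death or discharge status.

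The SAP says of a different stay variable: "Due to the non-normality of all laboratory values and ICU length of stay, nonparametric Wilcoxon rank-sum tests were used to test for significance". It does not mention hospital stay. The same text describes liver transplantation (OLT), intra-operative blood loss as the primary outcome and 34 patients per group. The protocol describes endoscopic and neurosurgical procedures with 101 per group.

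**The concern.** A hospital stay ends either with discharge or with death, and the two mean opposite things. If only the number of days is kept, a patient who dies on day 2 and one who goes home on day 2 have the same value, and both count as favourable. An arm with more early deaths would then appear to shorten the stay. Because the extraction list holds no death or discharge field, the study database could neither reveal this nor correct for it.

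There is a lesser question about the test. Stays are often right-skewed, and a t-test on days is then less powerful than a rank test. The SAP's rank test for ICU stay points the same way, but only weakly, because that text describes transplantation.

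**Working it through.** **1. The plan's own figures.** The documents give no effect, SD, power or mortality for hospital stay, so there is no figure to reproduce. From the plan come 101 patients per arm, 1:1 allocation and two-sided 0.05. Stays, deaths and SDs below are assumptions.

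**2. Size of the death bias.** Let a fraction p die on day d and let survivors stay m days on average. The recorded mean is (1 − p) × m + p × d. The gap between two arms that differ only in mortality is therefore (p1 − p0) × (m − d).

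With m = 10 and d = 3:
- p = 0.10: 0.90 × 10 + 0.10 × 3 = 9.30 days
- p = 0.15: 0.85 × 10 + 0.15 × 3 = 8.95 days
- p = 0.20: 0.80 × 10 + 0.20 × 3 = 8.60 days

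The higher-mortality arm looks 0.35 day shorter at 15% versus 10%, and 0.70 day shorter at 20% versus 10%. If m − d is 9 days instead of 7, the gaps are 0.05 × 9 = 0.45 and 0.10 × 9 = 0.90 day. At equal mortality the gap is zero.

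**3. Does the choice of test remove it?** A simulation used 101 per arm, lognormal stays with median 6 days and log SD 0.9, deaths on days 1 to 3, no treatment effect on the stay itself, and 6,000 trials per case. Rejection rates were:

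| Deaths | Shift in mean | t-test on days | Plain rank-sum | Rank-sum, deaths worst |
|---|---|---|---|---|
| 10% v 10% | 0.01 day | 4.2% | 4.9% | 5.4% |
| 10% v 15% | −0.37 day | 5.5% | 7.7% | 9.5% |
| 10% v 20% | −0.75 day | 8.9% | 17.9% | 23.2% |

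With unequal deaths, the excess rejections of the first two tests favour the arm with more deaths, and the plain rank test is worse than the t-test. Ranking deaths worst turns the direction round. In a separate run at 10% versus 20% (log SD 0.8), the probability that the higher-mortality arm had the better outcome was 0.547 on days as recorded and 0.449 with deaths ranked worst.

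**4. Power of the candidate tests.** Simulation with 101 per arm, lognormal stays, median 8 versus 6 days (ratio 0.75), and deaths on day 3 at the same rate in both arms. The rank test is plain where there are no deaths; otherwise deaths are ranked worst.

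| Log SD | No deaths: t v rank | 10% deaths: t v worst-rank | 20% deaths: t v worst-rank |
|---|---|---|---|
| 0.7 | 73% v 81% | 65% v 64% | 57% v 44% |
| 0.8 | 59% v 69% | 54% v 53% | 46% v 37% |
| 1.0 | 35% v 49% | 33% v 36% | 29% v 25% |

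Repeat runs agreed to within about 3 points. The rank test gains 8 to 14 points when nobody dies. The gain is gone, or nearly so, at 10% mortality and becomes a loss at 20%.

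**5. Validity of the t-test.** With no effect and no deaths, the t-test on days rejected 3.9% to 5.2% of the time at 34 or 101 per arm (log SD 0.5 to 1.1). It keeps its level.

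**The case against.** **The plan does not actually say this.** Section III.F is one general sentence covering several outcomes. It specifies neither untransformed days nor a scoring of deaths, and the primary aim's t-test is framed "to detect a 100% increase in the geometric mean of the non-ROTEM group over the ROTEM group", so a t-test in this protocol need not mean raw data. This stands in part. A reader might infer that the protocol prescribes a t-test on raw days with deaths scored as short stays. It prescribes neither. But a field in days, no stated transformation, no death field and no death rule leave that as the natural reading, and the geometric-mean wording belongs to the primary aim.

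**The SAP does not show skew in this trial.** A reader might take the SAP's remark on ICU stay as evidence that hospital stay here is non-normal, or that a rank test is already planned. The text describes transplant patients and 34 per group, and Appendix 1 has no ICU-stay field. It suggests skew and no more. This objection stands.

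**Power is not a reason for the proposed analysis.** Once deaths are ranked worst, the advantage over the t-test shrinks or reverses (step 4). This stands too.

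**The bias is small and hypothetical.** It needs unequal early deaths, on which the documents say nothing. With median 8 and log SD 0.8, the mean is 11.02 days and the standard error of the difference is 11.02 × √(e^0.64 − 1) × √(2/101) ≈ 1.47 days, so 0.35 and 0.70 day are about 0.24 and 0.48 standard errors. That limits the seriousness. It does not remove the point, because the direction is wrong and the planned data could not show it.

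**Conclusion.** The point holds as a minor gap. The protocol names a t-test/ANOVA for hospital stay, records days only, collects no in-hospital death and gives no death rule; the SAP leaves hospital stay out. If early deaths differ between arms, the arm with more deaths looks better by about 0.35 to 0.45 day at 15% versus 10%, and 0.7 to 0.9 day at 20% versus 10%. This rests on assumed mortality and on survivors staying 7 to 9 days longer than those who die. At equal death rates there is no bias.

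Two stronger conclusions are tempting and should not be drawn. The t-test is not invalid: it keeps its type I error. Nor is switching to a plain rank test the remedy: it leaves the death bias in place, and its power gain of about 8 to 14 points (assumed log SD 0.7 to 1.0) applies only when deaths are few. Stay is a secondary outcome with no power claim, so this is a cheap improvement and not a threat to the trial's main result.

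**What to change.** - Add in-hospital death (yes/no) to Appendix 1.
- Name one analysis of hospital stay. Either analyse time to live discharge with death as a competing event, or use a rank-sum test with in-hospital deaths given the worst rank.
- Report in-hospital deaths by arm next to the stay result, with medians and interquartile ranges.
- Reconcile the SAP with the protocol, so that it covers hospital stay in the population and sample size of this trial.

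The cost is one chart-extracted field and a few sentences. The result is no longer a difference in mean days, and a worst-rank result mixes mortality with stay, which is why deaths should be shown separately. With equal mortality of 10% to 20%, the worst-rank test has about the same or less power than the t-test (43% to 44% versus 57% to 58% in the least favourable case run, log SD 0.7 and 20% deaths). The power of the competing-event analysis was not simulated.
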